## 4.8 IMAGING ASSESSMENTS

Disease assessment will include imaging (computed tomography, magnetic resonance imaging) and physical examination (as indicated for palpable/superficial lesions). At screening, an MRI or CT of the head is required. At minimum, CT of the chest, abdomen and pelvis are required but additional imaging of affected areas (neck or extremities) may be required for documentation of target lesions.

Disease assessment will be completed within 35 days prior to the first dose of study drug, then as indicated in the Time and Events Tables Section 4.3. It is not necessary to repeat radiologic assessments at the final study visit if the subject was withdrawn due to disease progression. More frequent disease assessments may be performed at the discretion of the investigator. To ensure comparability between baseline and subsequent assessments, the same method of assessment and the same technique will be used when assessing response.

Disease response will be recorded as complete response (CR), partial response (PR), stable disease (SD), or progressive disease (PD) according to RECIST 1.1 criteria .

### 4.9.1 Surgical Ease Surveys

Assessment of surgical ease or difficulty after neoadjuvant therapy administration is not currently well understood. In order to obtain data on this important subject, we will be asking collaborating surgical oncologists to complete surveys on the subjective difficulty or ease of surgery compared to comparable surgery in patients who have not undergone neoadjuvant therapy. Surveys will be administered at time of patient trial enrollment, within 1 week of surgical resection and approximately 30 days after surgery is complete. These time-points are selected with the hope of obtaining initial thoughts on surgical difficulty and how this is altered by the neoadjuvant treatment. The 30-day post-operative survey is to capture complications, if any. Sample surveys are located in Appendix D. The surveys will be performed for the purpose of determining if neoadjuvant treatment influences the outcomes of surgery. Data will be recorded utilizing the Prometheus database.

## 5.0 ADVERSE EVENTS AND SERIOUS ADVERSE EVENTS

An adverse event is the appearance or worsening of any undesirable sign, symptom, or medical condition occurring after the first protocol intervention, even if the event is not considered to be related to study treatment. Medical conditions/diseases present before starting study therapy are only considered adverse events if they worsen after starting study treatment. Abnormal laboratory values or test results constitute adverse events only if they induce clinical signs or symptoms, are considered clinically significant, or require therapy.

The investigator (or physician designee) is responsible for verifying and providing source documentation for all adverse events and assigning the attribution for all adverse events for subjects enrolled.

---

### Recommended Adverse Event Recording Guidelines

Attribution	Grade 1	Grade 2	Grade 3	Grade 4	Grade 5
Unrelated	Phase I	Phase I	Phase I Phase II	Phase I Phase II Phase III	Phase I Phase II Phase III
Unlikely	Phase I	Phase I	Phase I Phase II	Phase I Phase II Phase III	Phase I Phase II Phase III
Possible	Phase I Phase II	Phase I Phase II Phase III			
Probable	Phase I Phase II	Phase I Phase II Phase III			
Definitive	Phase I Phase II	Phase I Phase II Phase III			

The Adverse Event Recording period will be from the first protocol intervention to 150 days after the last dose of study drug.

## 5.1 DEFINITION OF AN AE

Any untoward medical occurrence in a subject or clinical investigation subject, temporally associated with the use of a medicinal product, whether or not considered related to the medicinal product.

Note: An adverse event (AE) can therefore be any unfavorable and unintended sign (including an abnormal laboratory finding), symptom, or disease (new or exacerbated) temporally associated with the use of a medicinal product. For marketed medicinal products, this also includes failure to produce expected benefits, abuse, or misuse. Examples of events meeting the definition of an AE include:

- Exacerbation of a chronic or intermittent pre-existing condition including either an increase in frequency and/or grade of the

- condition
- New conditions detected or diagnosed after study treatment administration even though it may have been present prior to the start of the study
- Signs, symptoms, or the clinical sequelae of a suspected interaction
- Signs, symptoms, or the clinical sequelae of a suspected overdose of either study treatment or a concomitant medication (overdose per se will not be reported as an AE/serious adverse event [SAE]).

Events that **do not** meet the definition of an AE include:

- Medical or surgical procedure (e.g., endoscopy, appendectomy); the condition that leads to the procedure is an AE
- Situations where an untoward medical occurrence did not occur (social and/or convenience admission to a hospital).
- Anticipated day-to-day fluctuations of pre-existing disease(s) or condition(s) present or detected at the start of the study that do not worsen.
- The disease/disorder being studied or expected progression, signs, or symptoms of the disease/disorder being studied, unless more severe than expected for the subject's condition.

## 5.2 ADVERSE EVENT GRADING

Grading of AE's will be per the National Cancer Institute Common Terminology Criteria for Adverse Events (CTCAE v.5.0).

The following categories and definitions of causal relationship to study medication as determined by a physician should be used for adverse events:

- Definitive: There is a reasonable causal relationship between the study medication product and the AE. The event responds to withdrawal of study medication (re-challenge), and recurs with re-challenge when clinically feasible.
- Probable: There is a reasonable causal relationship between the study medication and the AE. The event responds to re-challenge. Re-challenge is not required.
- Possible: There is reasonable causal relationship between the study medication and the AE. Re-challenge information is lacking or unclear.
- Unlikely: There is a temporal relationship to study medication administration, but there is not a reasonable causal relationship between the study medication and the AE.
- Unrelated: There is not a temporal relationship to study medication administration (too early, or late, or study medication not taken), or there is a

- reasonable causal relationship between non-study medication, concurrent disease, or circumstance and the AE.
- The expression “reasonable causal relationship” is meant to convey in general that there are facts (eg, evidence such as de-challenge/re-challenge) or other arguments to suggest a positive causal relationship.

## 5.3 SERIOUS ADVERSE EVENT REPORTING (SAE)

Serious adverse event (SAE) is defined as one of the following:

- Is fatal or life-threatening
- Results in persistent or significant disability/incapacity
- Constitutes a congenital anomaly/birth defect
- Is medically significant, i.e., defined as an event that jeopardizes the patient or may require medical or surgical intervention to prevent one of the outcomes listed above
- Requires inpatient hospitalization or prolongation of existing hospitalization,
- Note that hospitalizations for the following reasons should not be reported as serious adverse events:
  - Routine treatment or monitoring of the studied indication, not associated with any deterioration in condition
  - Elective or pre-planned treatment for a pre-existing condition that is unrelated to the indication under study and has not worsened since signing the informed consent
  - Social reasons and respite care in the absence of any deterioration in the patient’s general condition

Note that treatment on an emergency outpatient basis that does not result in hospital admission and involves an event not fulfilling any of the definitions of a SAE given above is not a serious adverse event.

### ***SAE REPORTING***

The principal investigator has the obligation to report all serious adverse events to the FDA (if applicable), IRB, and Novartis Patient Safety Department (***For patients taking Novartis drugs***).

All events reported to the FDA by the investigator are to be filed utilizing the Form FDA 3500A (MedWatch Form), if applicable.

- To ensure patient safety, every SAE, regardless of suspected causality, occurring after the patient has provided informed consent and until at least 150 days after the patient has stopped study treatment or until the start of a new anti-neoplastic

medication if sooner than 150 days must be reported to Novartis within 24 hours of learning of its occurrence. If a subject starts a post-treatment antineoplastic therapy, then only adverse events suspected to be related to study treatment should be collected out to 150 days after discontinuation of PDR001. Reporting to Novartis should also occur within 30 days after the last dose of dabrafenib or 120 days after the last dose of trametinib, if the subject continued the combination partner more than 150 days after the last dose of PDR001). Information about all SAEs is collected and recorded on a Serious Adverse Event Report Form. The investigator must assess and record the relationship of each SAE to each specific study treatment (if there is more than one study treatment), complete the SAE Report Form in English, and **send the completed, signed form along with the Novartis provided cover sheet to the Novartis Patient Safety department by email ([contact]) within 24 hours.**

Any additional information for the SAE including complications, progression of the initial SAE, and recurrent episodes must be reported as follow-up to the original episode within 24 hours of the investigator receiving the follow-up information. An SAE occurring at a different time interval or otherwise considered completely unrelated to a previously reported one should be reported separately as a new event.

Any SAEs experienced after the reporting period described above period should only be reported to Novartis if the investigator suspects a causal relationship to the study treatment.

Follow-up information is submitted in the same way as the original SAE Report. Each re-occurrence, complication, or progression of the original event should be reported as a follow-up to that event regardless of when it occurs. The follow-up information should describe whether the event has resolved or continues, if and how it was treated, whether the blind was broken or not, and whether the patient continued or withdrew from study participation.

If the SAE is not previously documented in the Investigator's Brochure or Package Insert (new occurrence) and is thought to be related to the Novartis study treatment, an oncology Novartis Patient Safety department associate may urgently require further information from the investigator for Health Authority reporting. Novartis may need to issue an Investigator Notification (IN), to inform all investigators involved in any study with the same drug that this SAE has been reported. Suspected Unexpected Serious Adverse Reactions (SUSARs) will be collected and reported to the competent authorities and relevant ethics committees in accordance with Directive 2001/20/EC or as per national regulatory requirements in participating countries.

### ***PREGNANCIES***

To ensure patient safety, each pregnancy occurring while the patient is on study treatment must be reported to Novartis within 24 hours of learning of its

occurrence. The pregnancy should be followed up to determine outcome, including spontaneous or voluntary termination, details of the birth, and the presence or absence of any birth defects, congenital abnormalities, or maternal and/or newborn complications.

Pregnancy should be reported by the investigator to the Novartis Patient Safety department by email ([[contact]](mailto:[contact])). Pregnancy follow-up should include an assessment of the possible relationship to the study treatment and any pregnancy outcome. Any SAE experienced during pregnancy must be reported on the SAE Report Form.

Pregnancy outcomes must be collected for the female partners of any males who took study treatment in this study. Consent to report information regarding these pregnancy outcomes should be obtained from the mother.

### **Serious Adverse Event (SAE) Reporting**

An adverse event or suspected adverse reaction is considered “serious” if, in the view of either the investigator or the sponsor, it results in any of the following outcomes:

- Death
- A life-threatening adverse drug experience – any adverse experience that places the patient, in the view of the initial reporter, at immediate risk of death from the adverse experience as it occurred. It does not include an adverse experience that, had it occurred in a more severe form, might have caused death.
- Inpatient hospitalization or prolongation of existing hospitalization
- A persistent or significant incapacity or substantial disruption of the ability to conduct normal life functions.
- A congenital anomaly/birth defect.

Important medical events that may not result in death, be life-threatening, or require hospitalization may be considered a serious adverse drug experience when, based upon appropriate medical judgment, they may jeopardize the patient or subject and may require medical or surgical intervention to prevent one of the outcomes listed in this definition. Examples of such medical events include allergic bronchospasm requiring intensive treatment in an emergency room or at home, blood dyscrasias or convulsions that do not result in inpatient hospitalization, or the development of drug dependency or drug abuse (21 CFR 312.32).

- Important medical events as defined above, may also be considered serious adverse events. Any important medical event can and should be reported as an SAE if deemed appropriate by the Principal Investigator or the IND Sponsor, IND Office.
- All events occurring during the conduct of a protocol and meeting the definition of a SAE must be reported to the IRB in accordance with the timeframes and procedures outlined in “The University of Texas M. D. Anderson Cancer Center Institutional Review Board Policy for Investigators on Reporting Serious Unanticipated Adverse Events for Drugs and Devices”.

Unless stated otherwise in the protocol, all SAEs, expected or unexpected, must be reported to the IND Office, regardless of attribution (within 5 working days of knowledge of the event).

- **All life-threatening or fatal events**, that are unexpected, and related to the study drug, must have a written report submitted within **24 hours** (next working day) of knowledge of the event to the Safety Project Manager in the IND Office. -
- Unless otherwise noted, the electronic SAE application (eSAE) will be utilized for safety reporting to the IND Office and MDACC IRB.
- Serious adverse events will be captured from the time of the first protocol-specific intervention, until 150 days after the last dose of drug, unless the participant withdraws consent. Serious adverse events must be followed until clinical recovery is complete and laboratory tests have returned to baseline, progression of the event has stabilized, or there has been acceptable resolution of the event.
- Additionally, any serious adverse events that occur after the 150 day time period that are related to the study treatment must be reported to the IND Office. This may include the development of a secondary malignancy.

#### **Reporting to FDA:**

- Serious adverse events will be forwarded to FDA by the IND Sponsor (Safety Project Manager IND Office) according to 21 CFR 312.32.

**It is the responsibility of the PI and the research team to ensure serious adverse events are reported according to the Code of Federal Regulations, Good Clinical Practices, the protocol guidelines, the sponsor's guidelines, and Institutional Review Board policy.**

## **6.0 DATA MANAGEMENT**

For the purposes of this study data will be captured in a secure, password protected, encrypted and security compliant database (eg, CORe, Prometheus, MelCore). All patients will be registered in CORe before any study specific tests are performed. A brief explanation for required but missing data should be recorded as a comment. The investigator is required to retain, in a confidential manner, the data pertinent to the study for the duration of the study or the maximum period required by applicable regulations and guidelines or institutional procedures. If the investigator withdraws from the study (e.g., relocation, retirement), the records shall be transferred to a mutually agreed-upon designee (e.g., another investigator or IRB). Documentation of such transfer must be provided to the sponsor.

CORe, Prometheus, and Melcore are databases internally accessible to MD Anderson. Patient registration from all participating sites will be made through the CORe database. The Prometheus database will be used for clinical data capture on research participants, data entry on internal (MDACC) research patients will be performed by the MDACC's Department of Melanoma.

The study coordinator and investigators are responsible for ensuring that the eligibility checklist is completed in a legible and timely manner for every patient enrolled in the study, and that data are recorded on the appropriate forms and in a timely manner in the electronic case report forms (eCRFs) in the Prometheus database. All source documents will be available for inspection by the FDA and the MDACC IRB.

## 6.1 RECORDS RETENTION

Following closure of the study, the investigator must maintain all site study records (except for those required by local regulations to be maintained elsewhere) in a safe and secure location. The records must be easily accessible when needed and must be available for review in conjunction with assessment of the facility, supporting systems, and relevant site staff.

The investigator must retain investigational product disposition records, source documents, and case histories designed to record all observations and other data pertinent to the investigation (e.g. medical records) for two years. The records must be available for review in conjunction with assessment of the facility, supporting systems, and relevant staff.

## 7.0 DATA ANALYSIS AND STATISTICAL CONSIDERATIONS

### Overview

This will be a Phase II, open-label study of dabrafenib in patients with clinical Stage III melanoma who harbor a BRAF V600E or V600K mutation. In patients who achieve a pCR at the time of surgery, they will continue on dabrafenib and trametinib in the adjuvant setting. For those patients who do not achieve a pCR at the time of surgery, they will be treated with dabrafenib, trametinib and spartalizumab in the adjuvant setting.

The primary objective is to independently determine the 12-month relapse-free survival (RFS) rate in stage IIIB/C/D melanoma patients who, after 8 weeks of neoadjuvant dabrafenib and trametinib, do not achieve a pCR and receive adjuvant dabrafenib, trametinib and spartalizumab.

Secondary objectives include assessing safety in both the neoadjuvant and adjuvant settings. Recurrence patterns, including assessment of distant metastasis-free survival and overall survival separately by pathologic response status will also be addressed. The 12 month RFS of patients who achieve a pCR after receiving neoadjuvant and adjuvant treatment with dabrafenib and trametinib will also be assessed.

Exploratory objectives include assessing immune and molecular features of response and resistance, assessing the association between circulating blood markers and treatment response and relapse, and assessing surgical resectability.

A total of 45 patients will be initially treated with dabrafenib and trametinib for 8 weeks. Patients will be assessed for pCR as defined above based on the results of their surgical pathology. Patients who achieve a pCR will continue with the dabrafenib and trametinib combination for an additional 44 weeks. Patients who do not achieve a pCR will have spartalizumab added to dabrafenib and trametinib for an additional 44 weeks.

### **Sample Size and Power**

A sample size argument will be based upon patients who do not have a pCR. We expect approximately 60% of enrolled patients to not achieve a pCR after 8 weeks on the dabrafenib/trametinib combination. Historically, these patients experience a 12-month relapse-free survival (RFS) rate of 50%, and we hope to increase this to 75%. Under the assumptions of 2 years for patient accrual and an additional 2 years of follow-up after accrual ends, exponentially- distributed RFS times, and a two-sided exponential maximum-likelihood test with a 5% Type 1 error rate (alpha), a total of 24 non-pCR patients will provide 80% power to detect a minimum increase in RFS at 1 year to 75%. If 60% of patients do not have a pCR, we would need to enroll a total of 40 patients to have a total of 24 non-pCR patients, but to account for a potentially higher pCR rate and patient dropout, we will accrue a total of 45 patients.

### **Statistical Analyses**

For the primary objective, separately by group (patients who do/do not achieve a pCR at 8 weeks), the 12-month RFS rate will be estimated with a 95% confidence interval by using the Kaplan-Meier method. RFS is defined from time of surgery to any recurrence event (local or distant disease development or death due to melanoma. In addition, in patients who do not achieve a pCR, the 12-month RFS rate will be compared with the historical rate of 50% by using a two-sided exponential MLE test. Cox proportional hazards regression models will be fit to assess the association between various clinical, demographic, and disease covariates and RFS separately by pathologic response group.

For safety, the rate of grade 3+ adverse events will be tabulated and presented by group. For overall survival (OS) and distant metastasis-free survival (DMFS), 12-month rates will be reported with 95% confidence intervals, and Cox regression models will be used to assess the association between similar covariates as above and both OS and DMFS separately by group. OS is defined as time from treatment initiation to death. DMFS is defined as time from treatment initiation to development of documented distant metastatic disease outside the loco-regional site of the primary tumor or lymph node metastasis.

For the exploratory objectives, immunological and molecular features will be assessed quantitatively at baseline and at surgical resection. Kruskal-Wallis tests will be used to compare these parameters at each time point between responders (pCR) and non-responders (no pCR). Changes in each parameter from baseline to surgery will also be compared between responders and non-responders. Circulating tumor markers will be assessed at baseline and several on-study time points. Markers and changes in markers over time will be compared between responders and non-responders by using Kruskal-Wallis tests. In addition, generalized linear mixed models may be used to model these markers over time.

Finally, to assess the impact of neoadjuvant therapy on surgical resectability, a survey will be provided to surgeons regarding the difficulty of surgery (Appendix D). These data will be subjective and will be summarized graphically as numbers permit.

The Investigator is responsible for completing an efficacy/safety summary report, and submitting it to the IND Office Medical Affairs and Safety Group, for review and approval. Please submit efficacy and toxicity summary for the first 5 patients after 8 weeks of treatment and every 5 patients thereafter. Copy of the cohort summary should be placed in the Investigator's Regulatory Binder under "sponsor correspondence".

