### 2.2 SECONDARY OBJECTIVES

- To evaluate the safety of neoadjuvant dabrafenib and trametinib and adjuvant dabrafenib, trametinib and spartalizumab
- To determine the 12-month relapse free survival (RFS) rate in stage IIIB/C/D
- Melanoma patients who, after 8 weeks of neoadjuvant dabrafenib and trametinib, achieve a pCR and receive adjuvant dabrafenib and trametinib.
- To assess the recurrence patterns, distant metastasis-free survival (DMFS), and overall survival (OS) in all patients treated on protocol.

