### 3.0 STUDY DESIGN

[figure not shown]
This is an open-label single arm Phase II study that aims to examine the strategy of altering adjuvant therapy depending on pathologic response to neoadjuvant dabrafenib and trametinib therapy. Clinical stage III B/C/D BRAF V600E/K mutation with resectable disease will be enrolled. Patients will undergo 8 weeks of neoadjuvant dabrafenib and trametinib, followed by restaging scans and then definitive surgery if disease remains resectable. Surgical pathology will be analyzed for pathologic complete response (pCR), which is defined as absence of any residual tumor by H&E assessment.

Near pCR will be defined as less than 10% viable melanoma in the surgical specimen. Pathologic partial response (pPR) is defined as less than 50% viable tumor in the surgical specimen. No pathologic response (pNR) is defined as  $\geq 50\%$  viable tumor in the surgical specimen.

Patients who achieve a pCR will continue with adjuvant dabrafenib and trametinib for an additional 44 weeks in order to complete a total 1 year of therapy. Patients who do not achieve a pCR after 8 weeks of neoadjuvant dabrafenib and trametinib will receive dabrafenib, trametinib and spartalizumab in the adjuvant setting for a total of 44 weeks. Patients with no resectable disease after neoadjuvant therapy will be removed from the study and replaced.

Longitudinal blood and tumor will be collected in accordance with the study schedule.

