### **3.5 Adverse events of special interest (AESI)**

Adverse events of special interest include AEs of a potential irAE that are associated with spartalizumab treatment. An irAE may be experienced by subjects treated with spartalizumab due to its mechanism of action and predicted based on the reported experience with other immunotherapies that have a similar mechanism of action. Investigators must be vigilant and carefully identify AEs that may be suggestive of potential irAEs as their appearance may be sub-clinical and early diagnosis is critical for its adequate management and resolution.

An irAE is typically low grade and self-limited, often occurring after multiple doses, and most frequently involving the GI tract (diarrhea/colitis), skin (rashes), liver (hepatitis), lung (pneumonitis), kidneys (nephritis) and endocrine systems (a variety of endocrinopathies) and rarely CNS (encephalitis). Serological, immunological and histological assessments should be performed as deemed appropriate by the investigator, to verify the potential immune-related nature of the AE, and exclude a neoplastic, infectious or metabolic origin of the AE.

Severe grade or persistent lower grade irAEs typically require interrupting or permanently discontinuing treatment and administration of systemic steroids or other non-corticosteroid immunosuppressive medication when systemic steroids are not effective. Early recognition of irAEs and initiation of treatment are critical to reduce the risk of complications, since the majority of irAEs are reversible with the use of steroids and other immune suppressants.

In some cases, it may be unclear to determine if an adverse event is immune related or not, thus the following dose reduction guidelines should be followed.

The following sections address the specific instructions for mandatory dose modifications and recommended management for AEs considered suspected to be related to study treatment. For subjects who do not tolerate the protocol-specified dosing schedule, dose interruptions or modifications are mandated in order to allow subjects to continue study treatment.

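### The one safety analysis in the statistical section, grade 3+ events by pCR group, does not match a safety objective set by treatment phase and regimen

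*Combined protocol and SAP*

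**What the plan says.** Section 2.2 sets the objective by regimen: "To evaluate the safety of neoadjuvant dabrafenib and trametinib and adjuvant dabrafenib, trametinib and spartalizumab". The Section 7.0 Overview repeats it by setting: "Secondary objectives include assessing safety in both the neoadjuvant and adjuvant settings".

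Under Statistical Analyses, one sentence covers safety: "For safety, the rate of grade 3+ adverse events will be tabulated and presented by group". Group is introduced a few lines earlier, for the primary objective: "separately by group (patients who do/do not achieve a pCR at 8 weeks". No safety population, event window, phase split or table of immune-related events is given.

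Four other places bear on how that sentence would work:

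- Section 3.0, on patients who cannot be resected: "Patients with no resectable disease after neoadjuvant therapy will be removed from the study and replaced". What happens to their safety data is not stated.
- Section 5.0, Recommended Adverse Event Recording Guidelines: "The Adverse Event Recording period will be from the first protocol intervention to 150 days after the last dose of study drug". The table above that line has grade 1 and 2 events recorded in a Phase II trial when they are at least possibly related.
- Section 3.5: "Adverse events of special interest include AEs of a potential irAE that are associated with spartalizumab treatment". It adds: "An irAE is typically low grade and self-limited, often occurring after multiple doses".
- The end of Section 7.0 asks for an efficacy and toxicity summary to the IND Office for the first 5 patients after 8 weeks of treatment, and for every 5 after that.

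**The concern.** pCR status is known only after the neoadjuvant phase, and both pCR groups receive the same doublet before surgery. A table split on pCR is therefore not a table split on phase. It is a split on regimen only for the adjuvant phase, and only if everyone receives the assigned regimen.

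Three things are at stake. The neoadjuvant rate among all dosed patients is not produced. The rate that readers would take as the triplet rate includes events from before the first spartalizumab infusion. Low-grade immune-related events, the distinctive risk of adding an anti-PD-1 agent, have no planned summary.

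**Working it through.** The safety text states no figure to reproduce, so the check compares what the objective needs with what the table would contain. Sizes are added where the documents allow.

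**1. Group sizes.** The Sample Size section expects 60% of patients not to reach pCR. 24 / 0.60 = 40, as the plan states. With 45 enrolled, 45 x 0.60 = 27 non-pCR and 45 x 0.40 = 18 pCR.

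**2. Patients without pathology.** pCR is read from the surgical specimen, so a patient who is not resected has no result. The sentence leaves two readings:

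- The patient is in neither group and is missing from the table.
- The patient counts as not achieving a pCR and enters the non-pCR denominator without ever receiving spartalizumab.

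Neither gives a neoadjuvant rate among all dosed patients. The number affected is not stated, so I take a range from Section 1.2:

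- Lower end: in the interim report of the predecessor trial, every patient went on to surgery, which gives 0.
- Upper end: by September 2019, 32 of 37 treated patients had gone to surgery. (37 - 32) / 37 = 13.5%, and 0.135 x 45 = 6.1. This is an upper bound, because some of the five may still have been awaiting surgery.

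The range is 0 to about 6 of 45.

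**3. Doublet and triplet events in the non-pCR group.** Recording starts at the first protocol intervention, and the analysis sentence sets no narrower window. The 8 neoadjuvant weeks are 8/52 = 15% of planned treatment. More doublet-only time follows surgery: under Table 12, dabrafenib and trametinib restart ideally within 2 weeks of surgery, while spartalizumab is first marked at Week 12.

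Let T be the proportion with a grade 3+ event on the triplet and D the proportion with one in the neoadjuvant phase, assumed independent. The group rate is 1 - (1 - D)(1 - T). For T, I use the 78% with a grade 3 toxicity among 36 patients with metastatic disease (Section 3.3.1), standing in for grade 3+. The documents give no value for D, so I assume 10-30%.

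| D | Group rate | Excess over 78% |
|---|---|---|
| 10% | 1 - 0.90 x 0.22 = 80.2% | 2.2 points |
| 20% | 1 - 0.80 x 0.22 = 82.4% | 4.4 points |
| 30% | 1 - 0.70 x 0.22 = 84.6% | 6.6 points |

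As a cross-check, read 78% as the whole 52-week rate under a constant hazard h = -ln(0.22)/52. Then 1 - exp(-8h) = 21% have a first event in the 8 neoadjuvant weeks, and the 44-week rate alone is 1 - exp(-44h) = 72%. The gap of about 6 points lies in the same range.

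**4. Low-grade immune-related events.** Section 3.5 makes potential immune-related events the events of special interest and describes them as usually low in grade. Section 5.0 records them at grades 1-2 when related. The analysis begins at grade 3.

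These events can have consequences. Appendix B gives prednisone for grade 2 nephritis. Sections 3.3.2 and 3.8.2 both make spartalizumab discontinuation depend on steroid dose, and 3.3.2 also on non-recovery. The limits in those two sections differ and must be reconciled. Under either, a grade 2 event could end spartalizumab and not appear in the planned table.

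**5. Precision of separate tables.** With no events of a given type, the exact two-sided 95% upper limit is 7.9% for n = 45, 12.8% for n = 27 and 18.5% for n = 18.

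**The case against.** The strongest reply is that the plan is terse, not wrong.

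- **Other safety outputs exist.** A reader might infer that the grade 3+ table is the only safety output in the whole document. It is not. Section 7.0 also requires serial toxicity summaries starting after 8 weeks, the length of the neoadjuvant phase, and Section 4.9.1 captures surgical complications at about 30 days. This limits the point to the specified statistical analyses. It does not remove it: the summaries are oversight reports with no stated content or denominator, and neither output is a final analysis by regimen.
- **The plan does not say that anyone is excluded.** A reader might infer that patients who stop early for toxicity disappear from the report. The documents do not say so. The removal rule covers unresectable disease, a patient who stops drug may still be resected, and none of the five in the predecessor trial is shown to have left for toxicity. Misplacement in the non-pCR group is as natural a reading as omission.
- **The Overview commits to both settings.** Within the adjuvant setting, pCR group does correspond to assigned regimen, so a by-group table could be applied phase by phase. That would be sensible, but the analysis sentence does not say it.
- **The numerical bias is modest.** For 21 of 27 patients the exact 95% interval is 58-91%, so 2-7 points lie well inside sampling error. That stands. The greater loss is interpretive: the most common grade 3 toxicity in the metastatic triplet study was pyrexia (17%), which Section 3.3.3 links to dabrafenib with or without trametinib. A pooled rate cannot show what spartalizumab adds.
- **No frequency is given for low-grade events.** The description in Section 3.5 is qualitative, so it cannot be said that the grade 3 cut removes most immune-related events.

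**Conclusion.** The mismatch holds. As specified, the safety analysis does not deliver the neoadjuvant doublet rate in all treated patients, does not give a triplet rate free of doublet-only time, and includes no summary of grade 1-2 immune-related events.

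The sizes are illustrative. The count without pathology, 0 to about 6 of 45, is borrowed from the predecessor trial. The overstatement of about 2-7 points rests on a 78% triplet rate from metastatic disease, an assumed 10-30% neoadjuvant rate, and independence between phases.

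A reader might conclude that the trial cannot answer its safety objective. That goes too far: the related low-grade events are recorded, and the tables can be specified without new data. This is a fault in how a secondary analysis is specified. It does not touch the primary endpoint, but it should be corrected because the correction is cheap.

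**What to change.** Replace the safety sentence in Statistical Analyses with wording such as:

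> Adverse events will be tabulated by treatment phase and treatment actually received:
> (i) neoadjuvant dabrafenib and trametinib, in every patient given one dose or more, including patients not resected, withdrawn or replaced;
> (ii) adjuvant dabrafenib, trametinib and spartalizumab, in every patient given one spartalizumab dose or more, counting events from the first infusion;
> (iii) adjuvant dabrafenib and trametinib without spartalizumab, shown separately for pCR patients and for non-pCR patients before their first infusion or who never receive one.
> Each table reports grade 3+ events. Table (ii) also reports immune-related events of any grade.

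The second part of (iii) is needed so that a non-pCR patient who resumes the doublet but never starts spartalizumab does not fall between tables.

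The cost is wording and a few extra tables built from onset dates, dosing dates and grades. There is no added patient burden and no change to any clinical rule. The drawback is small denominators: about 45 for (i), 27 for (ii), and 18 pCR patients in (iii), less any who start no adjuvant therapy. The tables should therefore carry exact intervals and be read as descriptive.
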